#### **4.5.2c Master List**

A participant will be added to the master list of subjects when s/he is consented. This master list will be kept on the secure VA shared drive (only accessible to study staff) for this study. Only staff that are part of the study and have access to the shared drive, and thus will have access to this master list.

#### **4.5.2d VHA Health Records**

A VHA health record will not be created and updated for this study.

#### **4.5.2e Certificate of Confidentiality**

We will obtain a certificate of confidentiality for this research study.

### **4.6 Risk/Benefit Ratio**

#### **4.6.1 Potential Risks and Methods to be Used to Minimize Risks:**

- 1) During the study assessments and treatment, participants may experience some discomfort from discussing personal material and completing self-report questionnaires. Likewise, some participants may feel uncomfortable about having the study assessments and qualitative interviews related to *VetEd* app usage.
- 2) There is a risk of breach of confidentiality and loss of privacy, which great care will be taken to prevent. As discussed below, we will take precautions to ensure that potential risks are minimized.

## *Protection Against Risk*

- 1) In order to minimize anxiety during the study assessments, focus groups, or usability testing, the PI and study staff will make every attempt to help participants feel comfortable when discussing sensitive material or talking aloud during focus groups and qualitative interviews. The PI is a licensed clinical psychologist with 10 years of clinical experience, particularly with regard to treating student mental health concerns, PTSD, and depression.
- 2) Initial and continuing participation of the participant in these protocols will be strictly voluntary; the participant will remain free to terminate participation at any time.
- 3) Potential study participants will be screened initially over the phone for eligibility. For screening purposes only, this study will maintain a contact log. This log will contain the identifying information for veterans who are identified by research staff via medical record review or who contact research staff after learning about the study. It will contain the veteran's name, social security number, contact information, and status (No Response, Screened In, Screened Out, Pending, Chose not to participate). This log will be securely stored on a VA shared drive. This log will be maintained until the end of the recruitment period in order to prevent ineligible or uninterested veterans from being contacted again by letters from providers or by research staff. The identifiable information will be used only by members of the research team. This information will not be disclosed to anyone outside the VA. The proposed study poses minimal risk to the privacy of the subjects because:
  - Study screening forms will be coded, and will not contain the veteran's name, social security number, or date of birth.
  - All identifying information will be maintained in locked file cabinets in locked offices or on the study's secure VA server space.
  - Only identifying information for candidates who meet the diagnostic eligibility criteria will be recorded.
  - Identifying information for these veterans will be recorded electronically on the secure VA shared drive.
  - If Veterans are not interested, we will transfer their information to a log of non-interested participants which will also be recorded electronically on the study's secure space on the VA server.
  - This information will be only be used for scientific research purposes.
  - Only VA study team members will have access to this information.
  - The study team will not identify, directly or indirectly, any individual participant in any report of such research or otherwise disclose participant identities in any manner.

Following this initial screening, potential study candidates will be consented and then participate in a detailed psychiatric screening interview at the first study visit with trained project staff who are closely supervised by [name]. Effective screening will exclude Veterans who would be at greater risk because of psychiatric conditions revealed by this process. [name] has used the aforementioned screening criteria successfully in the past with behavioral intervention studies. If at any point there are significant adverse reaction during the screening process, the participant will be removed from the study and appropriate treatment implemented. This could include immediate assessment to a local emergency room.

- 4) There is a possibility that study participants will not improve their academic functioning after testing the mobile app. All participants who fail to respond to treatment or withdraw prematurely will be referred for alternative treatment. If withdrawal from the study is necessary, we will provide appropriate alternative treatments (e.g., placing a consult with the VITAL program or Mental Health Clinic). [name] will discuss the study, alternative treatments, or any concerns about the study with participants if requested by the participant or health care provider.
- 5) Participants may possibly experience clinical deterioration during the study. However, [name] will be available to participants by phone, or in person if necessary, to discuss any concerns throughout the treatment period. Drs. [name], [name], and [name] are all licensed psychologists, and will be available to study participants in the event of a clinical emergency; participants may also go to Bedford VA walk-in clinic if a clinical emergency occurs. This will be clearly communicated orally and in writing to study participants. Participants will be withdrawn from the study if their clinical condition deteriorates substantially. Participants may also be withdrawn if, in the judgment of the study investigators, remaining in the study poses a substantial risk to the participant or a higher level of care is needed.
- 6) Participants in the study may report suicidal ideation or suicidal intent. Given that some study participants may present with numerous vulnerabilities (e.g., history of traumatic brain injury, current or past suicidal ideation or behavior), all study staff members will be trained by [name], a licensed psychologist, in procedures for conducting risk assessment and crisis interventions. For participants who in the PI's judgment pose a substantial current risk of suicide but do not consent to having a provider contacted, we will breach confidentiality and contact their provider while notifying the participant of this and explaining our rationale (concern for their safety). At the beginning of the study and each subsequent assessment, participants will be told that the information they share is confidential unless the participant appears in jeopardy of harming themselves or someone else. For actively suicidal participants, or other participants who appear at high risk, who are not currently receiving mental health treatment, we will strongly encourage the participant to obtain mental health treatment. In addition, we will make every effort to find treatment for the participant and facilitate their obtaining treatment in a timely way.

*Telephone Risk Assessments.* Risk assessment will be conducted with all participants during the initial eligibility screening. Elements of risk assessment will include level of suicidal ideation and suicidal intent, using questions from the University of Washington Risk Assessment Protocol (UWRAP). If the Veteran endorses either of these items, further questions will be asked, including presence and level of specificity of a plan, access to weapons and other means, presence of known risk factors (e.g., recent loss, substance misuse, chronic pain or other serious medical problems), and presence or absence of deterrents. The PI will be notified of all such occurrences immediately. Following the procedures of the Bedford VAMC, if a Veteran is at imminent risk of suicide at the time of a phone screen, the RA will direct the Veteran to [name] or their clinician designee via warm telephone transfer. The psychologist will conduct a suicide risk assessment over the telephone in order to determine the Veteran's level of risk. If the psychologist deems the Veteran to be at imminent risk, s/he will call the police and request emergency services via a warm transfer. The psychologist will stay on the line with the Veteran until s/he makes contact with emergency services and care is transferred. In the unanticipated event that a licensed clinical psychologist is not available, and study staff are unable to reach the emergency room at the VA, they will conduct a warm transfer to the Veterans' Crisis Line. If they believe that the Veteran

is not at imminent risk, but may need a welfare check, s/he will coordinate with VA police and the suicide prevention team. We will coordinate with credentialed, clinical research staff at each study site to ensure that there is constant coverage by a licensed clinical psychologist. As necessary, the study team will collaborate with the local suicide prevention coordinator to facilitate care and clinical follow-up. If a potential participant is hospitalized, they will remain potentially eligible and will be invited to participate during or after their hospitalization.

7) Initial and continuing participation of the participant in these protocols will be strictly voluntary; the participant will remain free to terminate participation at any time.

8) All data collected from participants, CPRS/[VISTA](#)-review, or the mobile app will be used specifically for the research purposes described in this application. No identifying information will be associated with any information provided by participants as a function of their participation in this study, including their names, addresses, or phone numbers. Each participant in the study will be assigned an arbitrary study number at random and this number will be used for all data for subsequent analyses. Although the consent form will include the name of each participant, it will be filed separately from the actual data files for each participant. To ensure protection of confidential information, all data will be coded and stored in locked files to ensure confidentiality. Audio recordings of and video recordings (dependent on participant's chosen modality) of usability testing and focus groups will be kept at the data management site at the Bedford VA and stored on a secure VA shared drive for this study. Upon completion of the study and data entry and analysis, all data and files will be stored and archived indefinitely under lock and key. Information about substance use will not be made available to any party without the written informed consent of the participant and at the participant's request. Only the PI and the PI's research team will have access to the computerized data. Names will not be included on videotaped portions of the study, in computerized data files, or in any published reports. Case records will be reviewed only by study personnel or, if necessary, by institutional, state, or federal regulatory personnel. Research assistants and others working on this study will be educated about the importance of strictly protecting participants' rights to confidentiality.

9) Numerous safeguards will keep electronic data secure. Each subject will be assigned a code number so that should any non-study personnel gain access to the data, they will not know to whom the data belong. A secure password is required to access computers, and computer networks are on secured servers that meet or exceed federal confidentiality standards.

10) The Bedford VA has institutional policies requiring all clinical investigators and their key personnel to undergo mandatory training in human subjects research. The program includes all clinical researchers regardless of their source of funding. Researchers typically fulfill this requirement by completing Bedford VA research trainings.

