### 4.2 Inclusion of Vulnerable Subjects

The study population may be considered vulnerable because they may be economically disadvantaged. The veteran population includes individuals who are economically or educationally disadvantaged. The study keeps payments to participation at a minimum in order to avoid coercion based on economic conditions. In addition, the informed consent is written at a grade-school level of education to minimize the vulnerability of the educationally disadvantaged.

Vulnerable participants will also include those with diagnosed mental health disorders. These individuals may have impaired decision-making abilities. Acute exacerbations of psychiatric illness may

substantially impair decision-making abilities by decreasing level of understanding and reasoning. However, the level of capacity in those that are stabilized is likely to be much higher. This study is not focused on treatment for acute exacerbation and thus, plans to include veterans who are not in an acute symptomatic exacerbation. Therefore, the decision-making capacity is likely to be intact and will be assessed via the planned phone screen.

Another population to be included is that of the Veterans themselves. They are accustomed to taking and following direct orders, thus introducing a further need for researchers to prevent coercion either directly or indirectly. Veterans will be given ample time to read and consider informed consent, with other treatment options presented by investigators. Family members, significant others, and primary treatment teams may also be involved in the decision-making process if the Veteran wishes. They are also informed that refusal to participate will be accepted without hesitation at any time and will not change their eligibility for VA services, treatment, disability payments, or other related VA benefits. Research staff will evaluate each subject at the end of the phone screen (focus group and formative evaluation phases), focus group, or usability testing session to insure that they have not experienced significant distress or exacerbation of their symptoms as a result of their participant. The evaluation will consist of asking the subject about (1) feelings of distress and (2) desire for additional support because of distress. Anyone experiencing distress and desiring support will be provided with informal support and if necessary taken to formal providers (see Protection Against Risk section).

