### **4.4 Inclusion/Exclusion Criteria**

#### **Phase One: Focus Groups**

Inclusion criteria:

- 1) Enrolled in a minimum of at least 2 courses in a higher education setting within the past year
- 2) Current DSM-5 mental health disorder
- 3) Competent to provide informed consent
- 4) Owns a smart phone capable of supporting mobile apps
- 5) Are willing and able to read in English
- 6) Ages 18 and older

Exclusion Criteria:

- 1) Current or recent (within 1 month of study entry) moderate or severe DSM-5 alcohol or drug use disorder
- 2) Cognitive impairment that would interfere with participation
- 3) Severe suicidal ideation or a psychiatric hospitalization within the past month

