a. The research staff will access these patients' medical records only to determine whether they meet the study inclusion criteria and obtain address and phone contact information. We will also access SSNs ensure that we are identifying the right patient for contact. We will not open flagged records.

b. We will then send a letter to the Veteran to invite him/her to learn more about the study (attached to this application). The letter will contain contact information for the research team so the patient can contact the research team for more information. It will state that if we don't hear from the patient within two weeks, that we will call them about the study. It will also state that if patients do not want to be called, they can call our research staff and let us know. The identifiable information will be used only by members of the research team. This information will not be disclosed to anyone outside the VA.

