#### **4.5.1 Subject Identification and Pre-Enrollment Screening:**

We will obtain information through oral communication (telephone screening) with the prospective subject. The investigator will also obtain identifiable private information by accessing records (via CPRS or VISTA) to determine eligibility. Thus the exception to informed consent applies and no waiver of informed consent is necessary.

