**4.6.2.2 Data Safety Monitoring**

A DSMB is not required because multiple clinical sites will not be used, the study is not blinded, and interventions are not particularly high risk or vulnerable populations are not included.

**Responsibility for Data and Safety Monitoring:** [name] will have overall responsibility for monitoring the integrity of the study data and participant safety. Any difficulties that arise with Veterans related to self-disclosed safety issues or concerns will be discussed between the PI and the co-investigators (Drs. [name] and [name]). Additionally, the safety of research participants will be discussed in meetings with Drs. [name], [name], and [name], respective to their areas of expertise.

[name] will be monitoring adverse events involving data loss and adverse events related to the study. Adverse events will be monitored in the following ways:

**Procedures for Monitoring Participant Safety:** The PI will implement the following procedures to ensure data integrity and the safety of participants during the study:

- 1) Many elements of the research plan are intended to minimize the risks of study participation. These are detailed in the Research Design and Methods section and 2) “Protection Against Risks” in the Human Participants section above. For example, the study exclusion criteria exclude Veterans who are experiencing clinically significant suicidality or a psychiatric hospitalization within the past month. The PI will carefully monitor participants at each study visit to ensure that they do not experience clinically significant deterioration; if they do, the PI will reevaluate them and, if indicated, refer them for immediate non-study treatment (e.g., pharmacotherapy, counseling, inpatient, or residential treatment). The PI (or covering clinician in her absence) will be available to participants in the event of an emergency. In the event that serious medical or mental health complications should occur, consultation from emergency clinical services is immediately available at the Bedford VA Medical Center.
- 2) Weekly meetings will be held between Drs. [name], [name], [name], and other study staff. We will discuss and resolve any safety issues more frequently if necessary, as such issues arise, possible participant withdrawal from the study, or any safety concern.

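### Section 4.6.1 has staff invite hospitalized candidates during the admission, when section 4.4 excludes those admitted for psychiatric reasons or suicide risk

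*Combined protocol and SAP*

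**What the plan says.** Section 4.6.1 (Protection Against Risk, Telephone Risk Assessments) describes how suicide risk is handled at the phone screen: "Risk assessment will be conducted with all participants during the initial eligibility screening". It then covers warm transfer to a psychologist, emergency services, the crisis line and the suicide prevention coordinator. The paragraph closes with: "If a potential participant is hospitalized, they will remain potentially eligible and will be invited to participate during or after their hospitalization".

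Three other places bear on the same Veterans:

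- Section 4.4 lists this exclusion, in the same words, for Phase One and Phase Two: "Severe suicidal ideation or a psychiatric hospitalization within the past month".
- Section 4.2 says that the study "plans to include veterans who are not in an acute symptomatic exacerbation". It uses this to argue that decision-making capacity is likely to be intact.
- Section 4.6.2.2 offers the exclusion as an example of how risk is kept low: "the study exclusion criteria exclude Veterans who are experiencing clinically significant suicidality or a psychiatric hospitalization within the past month".

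**The concern.** Because the sentence ends the suicide-risk procedure, the admission it most naturally refers to is a psychiatric one or one for suicide risk. That is the admission section 4.4 is written to exclude. As written, the rule has staff approach a Veteran during an acute crisis to offer a study for which the Veteran cannot qualify at that time.

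Two things are at stake. One is participant safety: sections 4.2 and 4.6.2.2 rest their assurances about capacity and risk on keeping such Veterans out. The other is eligibility deviations, if an invitation leads to consent before anyone looks again at the exclusion. The analysis is not affected.

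**Working it through.** No figure in the plan needs reproducing. The check sets the invitation rule against the exclusion, case by case, and then asks whether any later step closes the gap.

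**Step 1. When the two rules disagree**

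| Time of invitation | Section 4.6.1 | Section 4.4, this criterion | Conflict |
|---|---|---|---|
| During a psychiatric admission | Invite | Excluded (hospitalization) | Yes |
| During an admission for imminent suicide risk | Invite | Excluded (severe ideation, hospitalization, or both) | Yes |
| Less than one month after a psychiatric hospitalization | Invitation allowed | Excluded | Yes |
| More than one month after, no severe ideation | Invitation allowed | Not excluded | No |
| Around a medical admission, no severe ideation | Invite | Not excluded | No |

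The conflict is confined to the first three rows. In those rows the required wait is one month for eligibility and zero for the invitation.

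**Step 2. Whether a later step requires a recheck before consent**

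- *Record review.* Section 4.5.1 says: "The investigator will also obtain identifiable private information by accessing records (via CPRS or VISTA) to determine eligibility". No second look is specified. For candidates found by chart review, section 4.5 puts the review first and then says: "We will then send a letter to the Veteran to invite him/her to learn more about the study". The review therefore predates a phone screen that leads to an admission.
- *Phone screen.* Section 4.1 pre-screens candidates by phone, section 4.5.1a bases the questions on the eligibility criteria, and section 4.5.2b sends the consent sheet after screening. None of these orders a repeat screen after an admission.
- *Contact log.* Sections 4.5.1a and 4.6.1 provide a screened-out status that prevents ineligible Veterans from being contacted again. Section 4.6.1 keeps the hospitalized candidate *potentially eligible*, which points away from that status.
- *Notice to the PI.* On suicide-risk answers, section 4.6.1 says: "The PI will be notified of all such occurrences immediately". Nothing ties that notice to the later invitation.
- *Check at consent.* Section 4.5.2b assesses orientation, understanding and voluntary choice. It does not ask about recent hospitalization or ideation.
- *Psychiatric interview.* Section 4.6.1 places it after consent, at the first study visit. Section 4.5.2 enrolls at consent, with participation following at once in both phases. Table 3 in section 3.4 lists the SCID-5 at baseline, also after consent.

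No step requires this criterion to be checked again between the admission and consent.

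**Step 3. What a one-month delay would cost**

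Section 3.3 gives 10 months for Phase 1 and 9 months for Phase 2. One month is 1/10 = 10% of the first and 1/9 = 11% of the second. Section 4.5 plans to recruit 60 Veterans for at most 36 in the study, a margin of 60 − 36 = 24.

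**The case against.** The best defense is that the two rules govern different events. Section 4.4 decides who may take part; the sentence in section 4.6.1 decides who may be asked, and *potentially eligible* leaves eligibility open. A candidate transferred to emergency services in mid-screen has either not finished the screen or has met the exclusion, so a sensible reader would expect screening to be passed afterwards. In Phase 2, the baseline SCID-5 and the psychiatric interview stand between consent and use of the app, and section 4.6.1 says this screening excludes Veterans at greater risk. Section 4.6.2.2 adds monitoring at each visit. The procedures themselves are mild: a 1.5-hour focus group and a four-week app test. On this view, adding a phrase that makes the sentence subject to 4.4 would be enough.

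Much of this stands. The sentence does not waive section 4.4, and staff who apply 4.4 would avoid a breach. The later safeguards limit harm, and the Phase 2 interview may catch an excluded Veteran before the app is issued.

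The timing problem remains. A psychiatric inpatient cannot be eligible during the admission, yet the text directs that the invitation may be made then. The expectation of a repeat screen is an inference, because no text orders one. The interview and the SCID-5 come after approach, consent and enrollment, and neither is said to ask about hospitalization in the past month.

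It is also fair to say that section 4.4 does not state whether the month runs from admission or discharge, or whether it applies to severe ideation as well as to hospitalization. The fix takes the cautious reading on both.

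**Conclusion.** The concern holds. For psychiatric and suicide-risk admissions, the instruction to invite *during* the stay contradicts section 4.4 in both phases, as does inviting within a month after a psychiatric hospitalization. It also undercuts sections 4.2 and 4.6.2.2. The fault lies in when staff are told to invite, not in the exclusion itself.

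The effect is small. The documents give no rate of hospitalization after a phone screen, and the judgment that few candidates are affected is an assumption. No sample-size or analysis figure changes. The point should still be fixed, because it concerns Veterans at suicide risk and the correction is cheap.

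**What to change.** Replace the closing sentence of the telephone risk assessment paragraph so that section 4.4 governs:

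> A candidate hospitalized for psychiatric reasons or suicide risk will not be invited during the admission. They may be re-contacted no sooner than one month after discharge, and invited only if the phone-screen questions on suicide risk and hospitalization, repeated at that time, show that the section 4.4 exclusion no longer applies. Candidates admitted for medical reasons, without severe suicidal ideation, may be invited during or after the admission.

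The cost is a short protocol amendment and, for a few candidates, a repeat of questions already on the phone screen. Those candidates are invited later. The recruitment margin and the phase lengths can absorb that delay.

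Counting from discharge is a choice that section 4.4 does not spell out. If the sponsor prefers another start date, section 4.4 should state it, and the sentence above should match.
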